9.7.3 Safety analysis

The assessment of safety will be based mainly on the frequency of adverse events, which includes all serious adverse events. All adverse events will be summarized with the coding term, severity, and relationship to study drug by frequency tables with the counts and percentage. In addition, serious adverse events will be listed with event narration. Medical history/current medical conditions and adverse events will be coded using the latest version of Medical dictionary for regulatory activities (MedDRA) terminology.

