Non-interventional Study Protocol
BI Study Number 1199-0303

c16462309-02

Proprietary confidential information © 2017 Boehringer Ingelheim International GmbH or one or more of its affiliated companies

Week# Visit	Baseline	Wk 4	Wk 16	Wk 28	Wk 40	Wk 52	Wk 64	Wk 76	Wk 88	Wk 100	
	1	2	3	4	5	6	7	8	9	10	
Variables			← 3-month interval →								
Allowed window		± 14 days	← ± 1 month →								
- Berlin Questionnaire-obstructive sleep apnea ⁴	X ^{&}			X		X		X		X	
- Echocardiography data-PH	X ^{&}			X		X		X		X	
Concomitant medications ⁵	X	X	X	X	x	x	X	X	X	X	
Record of anti-fibrotic drugs*	X ⁶	X	X	X	X	X	X	X	X	X	
Lung function*, ⁷	X ^{&}	X	X	X	X	X	X	X	X	X	
6MWT*	X ^{&}					X				X	
SGRQ*	X ^{&}	X	X	X	X	X	X	X	X	X	
CAT*	X ^{&}	X	X	X	X	X	X	X	X	X	
Acute exacerbation	X	X	X	X	X	X	X	X	X	X	
Safety reporting ⁸	← →										
Serological tests*, ⁹	X ^{&}		X			X		X		X	
Biomarkers*, ¹⁰	X					X				X	
Gene test*, ¹¹	X										

*Data will be collected, if applicable. All examinations and managements will be based on the discretion of the physician and regular practice.

#Data collection time points will follow visit schedule in clinical practice.

&Since this is an observational study, examinations and tests will be performed as judged appropriately by the treating physician according to local medical standards, and the results of interest that closest to the baseline will be registered only if those are available prior to baseline visit.

- Age, gender, race, education level, environmental/occupation exposures, height, weight, and BMI.
- HRCT, surgical lung biopsy, multidisciplinary team (MDT) diagnosis, and UIP pattern.
- Cough, dyspnea, fatigue, weight loss, dizziness, chest pain, anxiety, aching muscles and joints, clubbed fingers, require oxygen therapy (device), or others (according to physicians' judgment and should be specified on the CRF)
- STOP-Bang Scoring Model data will be collected to assess if patients have obstructive sleep apnea, and Berlin questionnaire results will only be collected from those with suspected/confirmed obstructive sleep apnea according to STOP-Bang Scoring Model.
- Concomitant medications used for treating comorbidities within 6 months prior to enrolment will be collected.
- Anti-fibrotic drugs (i.e., nintedanib and pirfenidone) used within 6 months before baseline will be recorded.
- Spirometry data include FVC, DLCO, SpO₂, TLC, IC, etc.
- OFEV relevant ADR (serious and non-serious), fatal AEs, and pregnancies.

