11.2 ADVERSE EVENT AND SERIOUS ADVERSE EVENT COLLECTION AND REPORTING

The investigator shall maintain and keep detailed records of all AEs in their patient files.

Collection of AEs

The study design is of non-interventional nature and the study is conducted within the conditions of the approved marketing authorization. Sufficient data from controlled interventional trials are available to support the evidence on the safety and efficacy of the studied BI drug. For this reason, the following AE collection and reporting requirements have been defined.

The following must be collected by the investigator in the paper CRF from signing the informed consent onwards until the end of the study:

- All adverse drug reaction (ADRs) (serious and non-serious),
- All AEs with fatal outcome,

All ADRs including those persisting after study completion must be followed up until they are resolved, have been sufficiently characterized, or no further information can be obtained.

The investigator should carefully assess whether an AE constitutes an ADR using the information below.

Causal relationship of adverse event

The definition of an adverse reaction implies at least a reasonable possibility of a causal relationship between a suspected medicinal product and an adverse event. An adverse reaction, in contrast to an adverse event, is characterized by the fact that a causal relationship between a medicinal product and an occurrence is suspected.

Medical judgment should be used to determine the relationship, considering all relevant factors, including the pattern of reaction, temporal relationship, de-challenge or re-challenge, and confounding factors such as concomitant medication, concomitant diseases, and relevant history.

Non-interventional Study Protocol
BI Study Number 1199-0303**c16462309-02**

Proprietary confidential information © 2017 Boehringer Ingelheim International GmbH or one or more of its affiliated companies

Arguments that may suggest a **reasonable causal relationship** could be:

- The event is **consistent with the known pharmacology** of the drug
- The event is known to be caused by or **attributed to the drug class**.
- A **plausible time to onset of the event** relative to the time of drug exposure.
- Evidence that the **event is reproducible** when the drug is re-introduced
- **No medically sound alternative etiologies** that could explain the event (e.g. preexisting or concomitant diseases, or co-medications).

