6.2.3 Safety Endpoints

- Frequency of adverse events and serious adverse events.

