10.4 Safety Endpoints

- Frequency of adverse events and serious adverse events.

All adverse events will be summarized with the coding term, severity, and relationship to nintedanib by frequency tables with the counts and percentage.

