11.5 Safety Analyses

- Frequency of adverse events and serious adverse events.
 - AEs and SAEs will be summarized as number of AEs, number of subjects with AEs and percentage of subjects with AEs. The summary will be further categorized by the seriousness, severity, causality, and outcome.
 - AE will be coded using the MedDRA dictionary. All adverse events will be classified using MedDRA terminology. The number of subjects and percentage of subjects will be computed by System Organ Class and Preferred Term to show the incidence of AE. The incidence of AE will be categorized by the severity. The incidence of AE by the severity will be presented as a separate table. Number of events and number of subject with events will be included in the summary table.
 - The incidence of AEs suspected related to nintedanib will be computed per the MedDRA terms. Number of suspected events and the number of subjects with suspected event with the corresponding percentage will be listed. The incidence of AEs suspected related to nintedanib will also be categorized by the severity.

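### Safety analysis is described as AE/SAE incidence, but the CRF rule requires only ADRs and fatal AEs, and no nintedanib-specific denominator is stated for nintedanib-suspected events

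*Protocol*

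**What the plan says.** **Analysis side.** Protocol 9.7.3 reads: "The assessment of safety will be based mainly on the frequency of adverse events, which includes all serious adverse events". The SAP endpoint (6.2.3) is "Frequency of adverse events and serious adverse events". SAP 10.4 adds: "All adverse events will be summarized with the coding term, severity, and relationship to nintedanib by frequency tables with the counts and percentage". SAP 11.5 says: "The number of subjects and percentage of subjects will be computed by System Organ Class and Preferred Term to show the incidence of AE", and later: "The incidence of AEs suspected related to nintedanib will be computed per the MedDRA terms".

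**Collection side.** Protocol 11.2 opens its CRF rule with "The following must be collected by the investigator in the paper CRF" and lists two items: "All adverse drug reaction (ADRs) (serious and non-serious" and AEs with fatal outcome. Records of all AEs are to be kept in the patient files. The visit lists in Protocol 9.2.3 and footnote 8 of Table 1, repeated in SAP 7.1.1, are narrower on ADRs: "OFEV relevant ADR (serious and non-serious), fatal AEs, and pregnancies". SAP 5 limits the SAP to data collected on paper CRFs.

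**Passages that point one way or the other.** Protocol 9.7.4 describes the safety analysis as covering ADRs, AEs it calls fetal (apparently a slip for fatal) and pregnancy, which is the narrow scope. Protocol 9.10.2.1 lists SAEs in general, separately from ADRs, among paper-CRF data to be derived from source documents. Protocol 9.8 has staff preserve on the CRF whatever safety information arises. Both suggest wider capture.

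**Denominators.** SAP 8.3 defines one population, all eligible patients. SAP 8.4 and 9 split every table into patients with and without any anti-fibrotic record, pooling nintedanib and pirfenidone. SAP 9 bases percentages on subjects with valid assessments and says population sizes will be annotated in the tables. SAP 10.1 summarises exposure by drug. SAP 13.1 refers to mock-up tables that are not supplied.

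**The concern.** The analysis text promises more than the collection rule guarantees. A site that follows Protocol 11.2 exactly may leave a non-fatal hospitalisation judged unrelated to any drug off the CRF. A table described as AE or SAE incidence would then be read as something it is not.

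The two columns also fill differently. Where no anti-fibrotic drug is used, there are no current OFEV reactions to report, so under footnote 8 that column would hold essentially fatal AEs. Part of any difference between the columns would come from the collection rule.

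For nintedanib-suspected events, the natural question is what share of nintedanib-treated patients had one. The SAP text does not say that the percentage will be calculated on those patients.

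**Working it through.** **1. Is there a figure to reproduce?** No. The documents give no AE rate, no event count and no number of nintedanib or pirfenidone users. The first part is a comparison of text; the second is an identity illustrated with assumed values.

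**2. Which events are guaranteed to reach the tables?** The requirement in each place:

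| Event type | Protocol 11.2 (CRF rule) | Footnote 8 and visit lists | Protocol 9.7.3, SAP 6.2.3, 10.4, 11.5 (analysis) |
|---|---|---|---|
| ADR, serious or not | required | required if OFEV-relevant | included |
| Fatal AE, any cause | required | required | included |
| Non-fatal SAE, not drug-suspected | not required | not required | included |
| Non-fatal, non-serious AE, not drug-suspected | not required | not required | included |

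The last two rows are the gap. Protocol 9.10.2.1 would close the SAE row if it were meant as a collection rule, but it is written as a list of data to be traced to source.

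If sites collect exactly what 11.2 requires, every non-fatal record is drug-suspected by construction. In the SAP 11.5 breakdown by causality, only fatal events could then be unrelated. In the breakdown by outcome, the fatal share would be raised, because fatal events enter whatever their cause and non-fatal ones only if suspected.

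The size of the shortfall cannot be computed from the documents. As an illustration, assume 40% of patients truly had an SAE, and that a fraction f of those patients had one that was drug-suspected or fatal. The table would show 40% × f: 10% at f = 25%, 20% at f = 50%, 30% at f = 75%.

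**3. The denominator for nintedanib-suspected events.** Let N be the pooled anti-fibrotic column, N_nin the patients in it who used nintedanib, and p = (N − N_nin)/N the pirfenidone-only share. If x patients have a suspected event and all of them are among N_nin:

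printed % = x/N = (x/N_nin) × (1 − p), so the relative understatement is p.

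With an assumed x/N_nin of 40%:

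| p (assumed) | Printed % |
|---|---|
| 0% | 40.0 |
| 10% | 36.0 |
| 30% | 28.0 |
| 50% | 20.0 |

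A second illustration takes 10 affected patients, 60 anti-fibrotic users and 30 nintedanib users (all assumed) among the planned 100 or so. The result is 10/100 = 10.0% of eligible patients, 10/60 = 16.7% of anti-fibrotic users, or 10/30 = 33.3% of nintedanib users. The last two agree with the identity: p = 30/60 = 50%, and 33.3% × 0.5 = 16.7%.

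**4. Do numerator and denominator match?** Not automatically. The protocol records anti-fibrotic use in the 6 months before baseline, whereas SAP 8.4 groups patients by records during observation. A patient whose only nintedanib use was before baseline could have a suspected event after consent and yet be counted outside the exposed group. The definition has to settle this case.

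**The case against.** Much of the defence stands. Protocol 9.7.4 already gives the narrow scope within the analysis chapter, and 11.2 explains limited collection by the evidence available from controlled trials. The restriction is therefore a declared design choice, and the broad wording in 9.7.3 and the SAP may be loose drafting. Because SAP 5 and 8.10 confine the analysis and coding to what is on the CRF, AE can be read as recorded AE. The study is not a PASS, safety is in neither objective, and no test between the columns is planned.

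Four stronger readings are tempting, and the documents do not support them:

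- *The tables will contain only ADRs and fatal AEs.* Protocol 11.2 sets a minimum, and 9.8 and 9.10.2.1 leave room for more.
- *The tables are mislabelled.* Titles and footnotes belong to the mock-up tables, which are not supplied. Only the SAP prose can be criticised.
- *The SAP has no exposure-based denominator.* Its columns are defined by anti-fibrotic exposure. What is missing from the text is a nintedanib-specific one. A percentage of a clearly labelled pooled column is not wrong; it answers a different question.
- *The nintedanib percentage will be understated.* That depends on the pooled column being the denominator and on p being above 0. Neither is known.

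The difference between 11.2 and footnote 8 over which drug's reactions count should also not be pressed hard. The text introducing the 11.2 list refers to the studied company drug, and the expedited-reporting table in the same section names OFEV.

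What survives is that the passages disagree about which events are collected, and that the SAP text leaves the nintedanib denominator open.

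**Conclusion.** The point holds as a minor one. As written, the plan describes its safety output as the frequency or incidence of all AEs and SAEs, while its CRF rule guarantees only ADRs and fatal AEs. Percentages produced under that rule cannot be read as overall AE/SAE incidence, nor compared between patients with and without anti-fibrotic drugs. The size of the gap cannot be derived from the documents.

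The SAP text also states no nintedanib-specific denominator for nintedanib-suspected events. If the pooled column is used, the relative understatement equals the pirfenidone-only share, which is not given and could be 0; the percentages worked out above are illustrations. This part rests on the SAP text alone, since the mock-up tables may already address it.

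The effect is limited to descriptive safety reporting. The primary and secondary outcomes are not touched.

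**What to change.** 1. Reconcile Protocol 9.2.3 with Table 1 footnote 8 (and its copy in SAP 7.1.1), 9.7.3, 9.7.4, 9.8, 9.10.2.1 and 11.2 on which events go on the CRF. Correct the apparent slip in 9.7.4.
2. Describe and title the safety analyses in Protocol 9.7.3 and SAP 6.2.3, 10.4 and 11.5 by the events that the reconciled rule requires. Under 11.2 as it stands, these are ADRs and AEs with fatal outcome. If the narrow rule is kept, add a footnote that the two anti-fibrotic columns are not comparable, because the rule captures different events in each.
3. In SAP 11.5, make patients exposed to nintedanib the denominator for nintedanib-suspected events. State how patients with use only in the 6 months before baseline are counted, so that numerator and denominator match. Print that N and align the mock-up tables.

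**Cost.** If the narrow rule is kept: wording, titles, one footnote and one derived flag. No new data are needed, because nintedanib and pirfenidone use is already recorded and SAP 10.1 already summarises exposure by drug. The price is that no overall AE/SAE incidence can be claimed. If the reconciled rule instead requires all AEs and SAEs, the cost is in data collection: up to 10 scheduled visits × about 100 patients = about 1,000 patient-visits at which non-fatal events not suspected to be drug-related would also have to be captured.

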9.7.4 Handling of missing data

Imputation will be permitted for analyses of primary and secondary outcomes, if deemed appropriate and on a case-by-case basis, depending on the extent and distribution of missing values, and will be described in the SAP. In the analyses of the time-to-event endpoints, missing or incomplete data are managed by standard survival analysis techniques. It is not planned to impute missing values for safety analysis (ADR, fetal AE, and pregnancy).

All information already collected as part of the study will be retained for analysis; however, no further efforts will be made to obtain or record additional information regarding the patient.

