9.3.4 Study completion

The study will be considered completed for an individual patient when he/she completes 100 weeks of study participation unless reasons for early termination are met (see Section 9.2.2).

The whole study will be completed after estimated 100 patients are enrolled and complete the data collection. Patients who are prematurely withdrawn from the study will not be replaced by an equal number of newly enrolled patients.

A complete end of study visit must be performed for any patient discontinuing study participation. If a patient discontinues the study prematurely, another follow-up assessment should be performed if possible (unless the reason for discontinuation is erroneous enrolment of the patient into the study at baseline). All relevant information, including date, vital status, and the reason for discontinuation, must be recorded on the appropriate page of CRF of the next planned visit.

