9.7 DATA ANALYSIS

Analyses will be performed by a designated CRO. The main analysis population will consist of all eligible patients (i.e. all patients who have signed the informed consent and fulfilled all inclusion criteria and no exclusion criteria).

Analytic specifications, including tables and listings, will be detailed in the statistical analysis plan (SAP) that is separate from the full study protocol and will be updated over time as necessary. A change to the data analysis methods described in the study protocol will require an amendment only if it changes a principal feature of the study objective. Additional exploratory analyses of the data will be conducted as deemed appropriate.

Descriptive analyses will be performed to gain an understanding of the characteristics of the sample studied. Summary statistics of continuous variables will include number, mean,

standard deviation, minimum, Q1 (lower quartile), median, Q2 (upper quartile), maximum value, and 95% confidence intervals, as appropriate.

Tabulations of categorical variables will present all possible categories and display the absolute and relative frequencies. Estimates will be presented with 95% confidence intervals.

Statistical analysis of all data will be performed using the latest version of SAS[®] statistical software (SAS Institute, Cary, NC, USA) or other commercially available standard statistical software.

For analysis of primary and secondary outcomes (spirometry tests, SGRQ, CAT, and 6MWT), imputation will be permitted, if deemed appropriate and on a case-by-case basis, depending on the extent and distribution of missing values, and will be described in the SAP. All information already collected as part of the study will be retained for analysis; however, no further efforts will be made to obtain or record additional information regarding the patient.

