9.9 LIMITATIONS OF THE RESEARCH METHODS

Data collection

A non-interventional study is the most suitable design for obtaining information about the use of medicines in everyday therapeutic practice and thus for clarifying prospectively questions in everyday therapeutic practice. In addition, the observational design intends to collect available data that are recorded on medical charts. The lack of data of interest may be one of the limitations.

Missing data will be handled for primary and secondary outcomes as appropriate on a case-by-case basis, depending on the extent and distribution of missing values (see Section 9.7.4). All efforts will be made to minimize missing data and loss to follow-up in patients who are enrolled. For instance, before start of data collection, a study initiation visit will be performed for each medical center, where investigators and site staffs will be trained for study implementation, data collection, and safety reporting, etc. Investigator and site staff should escalate issues that can potentially jeopardize study outcomes to sponsor or CRO upon awareness. Sponsor, CRO, and site should work closely to manage any risks.

Selection bias

The entry criteria are non-restrictive and will permit the enrolment of a broad patient population. The choice of treatment is at the discretion of the investigator. Selection bias could occur at both the site (physician) level and the patient level. To minimize the site level selection bias, the goal is to have participating centers (i.e., medical center of Taiwan) that are representative for managing IPF patients in Taiwan and have access to all available treatment options for IPF that are approved for use in Taiwan.

Selection bias at the patient level could occur if sites preferentially enroll specific patients into the study. To minimize selection bias at the patient level, consecutive enrolment is performed.

Small sample size

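### Protocol 9.7 and 9.7.4 rule out further information-gathering for every patient, against 9.3.4, 9.9 and 11.2; deaths after loss can go unrecorded, so crude mortality is understated, and Kaplan-Meier survival is overstated only if loss is informative

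*Protocol*

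**What the plan says.** Two sections of the protocol carry the same instruction. Section 9.7 reads "All information already collected as part of the study will be retained for analysis; however, no further efforts will be made to obtain or record" more, and 9.7.4 repeats that "no further efforts will be made to obtain or record additional information regarding the patient". In both places the sentence follows text on imputation and missing data. Neither place ties it to withdrawal of consent, database lock or any other event.

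Other sections point the other way:

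- Protocol 9.3.4: "A complete end of study visit must be performed for any patient discontinuing study participation". It adds: "If a patient discontinues the study prematurely, another follow-up assessment should be performed if possible". It also says: "All relevant information, including date, vital status, and the reason for discontinuation, must be recorded", on the CRF page of the next planned visit.
- Protocol 9.9: "All efforts will be made to minimize missing data and loss to follow-up in patients who are enrolled".
- Protocol 11.2: "All ADRs including those persisting after study completion must be followed up until they are resolved", sufficiently characterised, or no more can be learned.

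The rules that decide what happens to a patient who stops attending are elsewhere. Protocol 9.1 and SAP 7.1 end observation at death, lung transplantation, two years or loss to follow-up. Protocol 9.7.1 censors patients without a documented death when last known alive at last contact. SAP 10.3 uses the last valid date among last anti-fibrotic dose, last contact and last visit. Mortality and time to death are a secondary outcome (Protocol 9.3.2.2), to be reported by Kaplan-Meier with incidence (9.7.1).

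**The concern.** Ten centres cannot follow both sets of instructions in the same way. A site that takes 9.7.4 literally stops looking once a patient leaves. A site that follows 9.3.4 makes a further assessment and records vital status. Even under 9.3.4, vital status is asked for once, around discontinuation, and no section carries it forward to Week 100. A patient who is lost at Week 30 and dies at Week 60 can therefore appear in the data as alive and censored.

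Two results are exposed. The first is the count and proportion of deaths, with their causes. The second is the Kaplan-Meier curve, if leaving is related to prognosis. Survival is one of the reasons given for the study: Protocol 7 cites a median of 0.9 year in Taiwan against 3 years elsewhere. SAP 9 also splits every analysis by anti-fibrotic use, so unequal loss between those groups would carry into the comparison.

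**Working it through.** The documents give no dropout rate, expected number of deaths or survival target, so there is no plan figure to reproduce. What follows is an illustration.

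**Inputs from the documents.** Follow-up T = 100 × 7 / 365.25 = 1.916 years (Protocol 9.7.1). Median survival 0.9 or 3 years (Protocol 7). N about 100 (Protocol 9.5).

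**Assumptions.** Exponential survival. Patients leave alive at a constant rate c, chosen so that a set share is lost by Week 100 (20% in the main case; 10% and 30% as the range). After leaving, the death hazard is r times the hazard h before leaving (r = 0.5, 1, 2, 4). For each case h is set so that true median survival stays at 0.9 or 3 years. No death after leaving is recorded. Incidence is read as deaths over all enrolled, because the documents do not define it.

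**Formulas.**

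- Share lost alive = c/(h+c) × (1 − e^(−(h+c)T))
- Deaths recorded = h/(h+c) × (1 − e^(−(h+c)T))
- Kaplan-Meier limit, censoring at last contact = e^(−hT)
- True survival = e^(−(h+c)T) + c × (e^(−rhT) − e^(−(h+c)T)) / (h + c − rh)

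At r = 1 the last expression reduces to e^(−hT), so Kaplan-Meier is unbiased whatever share is lost.

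**Crude deaths, 20% lost, r = 1.**

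- Median 0.9 y: h = ln 2/0.9 = 0.770, c = 0.235. Recorded: 0.770/1.006 × (1 − e^(−1.927)) = 65.4 per 100. True: 1 − e^(−0.770 × 1.916) = 77.1 per 100. Missed: 11.7/77.1 = 15% of deaths.
- Median 3 y: h = 0.231, c = 0.147. Recorded 31.5 per 100; true 35.8 per 100.
- With 10% or 30% lost, recorded deaths are 71 or 59 (true 77), and 34 or 29 (true 36).

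**Kaplan-Meier survival at Week 100, 20% lost.**

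| Hazard ratio after leaving | Median 0.9 y: KM / true | Median 3 y: KM / true |
|---|---|---|
| 0.5 | 20.9% / 25.3% | 60.9% / 63.0% |
| 1 | 22.9% / 22.9% | 64.2% / 64.2% |
| 2 | 25.5% / 21.2% | 68.3% / 65.4% |
| 4 | 28.3% / 21.0% | 72.5% / 66.2% |

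For example, at r = 2 and a 0.9-year median, h = 0.714 and c = 0.225. KM is e^(−1.368) = 25.5%. True survival is 0.1655 + 0.225 × (0.0649 − 0.1655)/(−0.489) = 21.2%. The gap is 4.3 points; at a 3-year median it is 2.9. Over 10% to 30% lost and ratios of 2 to 4, the overstatement runs from about 2 to 11 points (0.9 y) and 1.5 to 9 points (3 y). For scale, the 95% half-width with 100 patients and no losses, 1.96 × √(S(1−S)/100), is 8 points at S = 22.9% and 9 points at S = 64.2%.

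**A one-sided remedy.** Suppose site records reveal later deaths but say nothing about survivors, who stay censored at loss. At r = 1 the estimated hazard at time t becomes h·e^(−ht) / [e^(−(h+c)t) + (1 − e^(−ct))(e^(−ht) − e^(−hT))]. Integrated to T with 20% lost and a 0.9-year median, survival reads 18.1% against a true 22.9%. Collecting deaths alone therefore creates a bias that was not there before.

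**The case against.** A reader might infer that missed deaths by themselves make the survival curve too favourable. The documents do not support that. At equal hazards 15% of deaths are missed in the 0.9-year case and the Kaplan-Meier bias is zero. The share of deaths missed does not determine the bias; the link between leaving and prognosis does. Informative loss is plausible in a progressive disease, but neither document states or quantifies it.

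It can also be said that the disputed sentence is not the main cause, and that is right. Protocol 9.1 ends observation at loss to follow-up, and the censoring rules do the rest. Removing the sentence alone would not recover a single death. The clash with 9.9 is mild, because the efforts named there are site training and escalation of issues. The clashes with 9.3.4 and 11.2 are direct.

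The protocol does have some provision for deaths. Date and cause are collected if death occurs (9.3.3.7), fatal adverse events are collected until the end of the study (11.2), and the data sources include discharge files and electronic records (9.4). Some later deaths will be picked up this way, so the figures above, which assume none is, are upper bounds on what is missed for a given loss rate. No section, however, tells a site to look once the patient has gone.

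The sentence may have been meant for patients who withdraw consent. That is the likeliest intention, but neither section says so.

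**Conclusion.** The contradiction is certain and rests on the text alone. Following 9.7 and 9.7.4 as written, together with the observation and censoring rules, lets deaths between loss and Week 100 go unrecorded. A crude death proportion is then understated whenever such deaths occur: about 12 per 100 at a 0.9-year median and 4 per 100 at 3 years, assuming 20% lost and equal hazards. If incidence were instead a rate per person-time, it would behave like the Kaplan-Meier estimate.

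Overstatement of Kaplan-Meier survival is conditional on patients who leave dying faster. At 20% lost and a hazard ratio of 2 it is about 4 points (0.9 y) or 3 points (3 y). Every size here depends on assumed loss and hazard ratios. The medians run from diagnosis while the study clock starts at enrolment, up to 6 months later, so they only bracket the case. This is an inexpensive improvement to a secondary outcome and does not affect the lung-function endpoints.

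**What to change.** 1. Reconcile Protocol 9.7 and 9.7.4 with 9.1, 9.3.4, 9.9 and 11.2, and with SAP 7.1 and 10.3. Limit the sentence to patients who withdraw consent, and say from when it applies.
2. For all other early stoppers, record vital status as of Week 100 from the site records already named in Protocol 9.4, as a date of death or a date last known alive. Use the same look-up for every such patient, whatever the outcome.
3. Use these dates in the time-to-death analysis, and amend the censoring rule in Protocol 9.7.1 and SAP 10.3 to match. State how lung transplant recipients are treated in that analysis, since 9.1 ends their observation at transplantation.
4. Report the number censored before Week 100 and the reasons, overall and by anti-fibrotic subgroup. Define incidence.
5. Keep the analysis censored at last contact as a sensitivity analysis, because records may reveal deaths more readily than survival.

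The cost is wording changes in both documents and one record look-up per early stopper by staff who already complete the CRF. No visit or test is added, so the study stays non-interventional. Deaths outside the hospital may still be missed.
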